
Study Procedures
	
Trial participants will be recruited via advertisements in community newsletters, websites and mainstream and social media, and through research volunteer registries, community organisations and health promotion services targeting women. After telephone screening for eligibility and upon giving informed consent, participants will complete a baseline survey including questions about general health and surveys related to secondary outcomes. They will wear an accelerometer device (ActiGraph) over 7 days to determine their baseline physical activity including average daily step count. They will then be randomly allocated to either the intervention group, (n=500), or a waitlist control group, (n=500). Participants will complete a similar survey at 6 months post-randomisation and will wear the accelerometer again at 6 months post-randomisation for 7 days to determine end of program daily step count and physical activity. . Intervention participants will be invited to extend their participation in the study for a further 6 months to complete a similar survey and wear the accelerometer again at 12-months post-randomisation to determine daily step count and physical activity maintenance. Completion of this extra follow-up will be optional.
 
The intervention group will receive access to Active Women over 50 program, which includes telephone health coaching, email or SMS motivational messages incorporating several behaviour change techniques (BCTs), a program-specific website and a private Facebook page to support their physical activity. The control group will be waitlisted to receive the Active Women over 50 program after completing all 6-month follow-up measures.

Statistical Procedures Analysis Plan Sample Size
	
Analysis Plan
 
The primary outcome will be analysed using generalised linear regression to assess the effect of group allocation at 6 and 12 months, with its corresponding baseline score as a covariate. Continuous secondary outcomes will be analysed using linear regression, adjusting for the corresponding baseline measure of the outcome variable as appropriate. We will use log-binomial regression to determine the between-group difference in the proportion of people increasing daily steps by 2000+. Fall rates will be analysed using negative binomial regression models to estimate the difference in rates between groups after 6 months. There

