### **7.2 Statistical Analysis**

Analyses will be guided by a rigorous statistical analysis plan developed a priori as we have done previously and use an intention-to-treat approach. The primary outcome will be analysed using generalised linear regression to assess the effect of group allocation, with its corresponding baseline score as a covariate. Continuous secondary outcomes will be analysed using linear regression adjusting for the corresponding baseline measure of the outcome variable as appropriate. We will use log-binomial regression to determine the between-group difference in the proportion of people increasing daily steps by 2000+. Fall rates will be analysed using negative binomial regression models to estimate the difference in rates between groups after 6 and 12 months with exploratory analyses adjusting for amount of physical activity. There will also be pre-defined subgroup analyses included by age, rurality/remoteness of residence, number of medical conditions and baseline fall history. Analyses will be conducted using Stata 14 software.

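### The 6-month fall-rate model names no adjustment for baseline fall history, a variable the trial already has; adding it would gain some precision at no cost

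*Protocol*

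**What the plan says.** Section 7.2 sets the adjustment outcome by outcome. Daily steps are modelled "with its corresponding baseline score as a covariate". For the other continuous measures, "Continuous secondary outcomes will be analysed using linear regression adjusting for the corresponding baseline measure of the outcome variable as appropriate". For falls, "Fall rates will be analysed using negative binomial regression models to estimate the difference in rates between groups after 6 and 12 months", and the sentence continues "with exploratory analyses adjusting for amount of physical activity". No baseline term is named for the main falls model. The protocol synopsis, under the analysis plan, does not name one either: "Fall rates will be analysed using negative binomial regression models to estimate the difference in rates between groups after 6 months".

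The next sentence of 7.2 shows that a fall-history variable will exist: "There will also be pre-defined subgroup analyses included by age, rurality/remoteness of residence, number of medical conditions and baseline fall history". Section 5.5 stratifies randomisation by rural or urban location only. Section 7.2 also refers to a separate plan: "Analyses will be guided by a rigorous statistical analysis plan developed a priori". That plan is not at hand.

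**The concern.** Past falls may predict future falls. If they do, a model without fall history leaves that between-woman variation in the negative binomial dispersion, and the interval for the rate ratio is wider than it need be. The protocol applies this reasoning to steps and to the continuous secondary outcomes, but for falls it names only an exploratory adjustment for physical activity.

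The loss matters somewhat because the sample size in section 7.1 is set for steps alone and no power is stated for falls. A precision gain that needs no further women or data is worth taking. It has to be specified in advance, since a covariate chosen after the data are seen carries less credibility.

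The point concerns the 6-month comparison only. The 12-month wording in the same sentence is a separate matter.

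**Working it through.** **The plan's own figures.** There is none for falls. The figure for steps reproduces: n per arm = 2 × (1.96 + 1.2816)² × 4200² / 1000² = 371, and 371 / 0.75 = 495 per arm, or 990 in total against the planned 1000. Its only use here is the number evaluable: 500 × 0.75 = 375 per arm. Section 6.5.3 gives 20% dropout instead of 25%, which would make it 400. The percentage variance cut below does not depend on n.

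**Assumed inputs, none from the protocol.** Middle case: control mean μ₀ = 0.4 falls per woman over 6 months, true rate ratio 0.7 (so μ₁ = 0.28), total dispersion α = 1.5, proportion of prior fallers p = 0.25, and rate ratio for prior fallers R = 2.5.

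**Unadjusted model.** Variance of the log rate ratio = [(1/μ₀ + α) + (1/μ₁ + α)] / n = (2.5 + 1.5 + 3.571 + 1.5) / 375 = 0.02419, so SE = 0.156.

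**Adjusted model.**
1. Squared coefficient of variation explained by history: c = p(1−p)(R−1)² / (1−p+pR)² = 0.1875 × 2.25 / 1.375² = 0.223.
2. Residual dispersion: a = (α − c) / (1 + c) = 1.277 / 1.223 = 1.044.
3. Cell means, non-fallers then prior fallers: control 0.291 and 0.727; intervention 0.204 and 0.509.
4. Cell information w = n_cell × m / (1 + a·m): control 62.76 and 38.76; intervention 47.23 and 31.16.
5. Variance = 1 / Σ[w₀w₁ / (w₀ + w₁)] over the two history strata = 1 / (26.95 + 17.27) = 0.02261, so SE = 0.150.

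**Gain.** 1 − 0.02261/0.02419 = 6.5%. This is worth 1/0.935 = 1.07 times the sample, or about 50 of 750 evaluable women. Power = Φ(|ln 0.7|/SE − 1.96) rises from 63.1% to 66.0%.

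**Dependence on the strength of fall history**, other middle-case inputs held:

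| R | c | a | Variance cut | Power, from 63.1% to |
|---|---|---|---|---|
| 1.5 | 0.037 | 1.411 | 1.2% | 63.6% |
| 2 | 0.120 | 1.232 | 3.8% | 64.7% |
| 2.5 | 0.223 | 1.044 | 6.5% | 66.0% |
| 3 | 0.333 | 0.875 | 9.1% | 67.2% |
| 4 | 0.551 | 0.612 | 13.7% | 69.4% |

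**Wider range.** With 0.25-0.6 falls per woman, dispersion 1.0-2.5, 25-35% prior fallers and R from 2 to 4, the variance cut is 2-19% and the power gain about 1-9 points. A second grid assumed 0.3-1.0 falls per person-year, conditional dispersion 1-2, 20-30% prior fallers, R from 1.5 to 4, a treatment rate ratio of 0.75 and 375-500 per arm. It gave a cut of 0.4-20% and a gain of 0.1 to about 9 points.

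**Simulation check (400 replicates per scenario).** Adjustment lowered the SD of the log rate ratio from 0.167 to 0.164 at R = 2 and from 0.177 to 0.169 at R = 4. Type I error of the unadjusted test was 4.3-5.2%. The Monte Carlo SE around 5% is √(0.05 × 0.95 / 400) = 1.1 points, so this is consistent with the nominal level.

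**The case against.** The strongest objection is that silence is not a decision. Covariates for a secondary count outcome are ordinary SAP content, 7.2 invokes an SAP, and the protocol nowhere says that the falls model is unadjusted or that fall history is excluded. This stands to the extent that a reader should not infer the term has been rejected. It does not remove the point, because 7.2 already sets covariates for steps, for the continuous secondaries and for an exploratory falls analysis. The uneven treatment is in the written text.

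A second objection is that fall history is not a true baseline score for this outcome. Falls are counted prospectively on monthly calendars, the assessment schedule (Table 3) shows no falls count at baseline, and the fall-history item and its recall period are not described. This also stands. A covariate need only be measured before randomisation and be predictive, but its definition has to be written down.

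Two stronger readings are tempting and are not supported:

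- *Chance imbalance in prior fallers makes the comparison unsound.* The SD of the between-arm difference in prior fallers is √(2 × 0.25 × 0.75 / 375) = 3.2 points. A 2-SD imbalance of 6.4 points at R = 2.5 shifts the unadjusted rate ratio by 0.064 × 1.5 / 1.375 = 7%. On the log scale that is 0.067, or 0.43 of the SE of 0.156. The unadjusted interval already allows for it.
- *The cost per fall prevented is affected.* Section 7.3 builds its ratios from arm means with bootstrapping and does not name this regression as an input.

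**Conclusion.** The point holds as an efficiency improvement on a secondary outcome. The main 6-month falls model as written names no baseline covariate, fall history is available, and the randomisation does not balance it. The unadjusted analysis is nevertheless valid, and no figure in the protocol is undermined.

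The usual gain is modest. It exceeds 5 power points only if prior fallers fall at roughly three to four times the rate of others, and it nearly vanishes if fall history is a weak predictor. All of these sizes rest on assumed fall rates, dispersion, prevalence of prior fallers and history effect. Whether the SAP already contains the term is unknown.

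**What to change.** In 7.2 and in the synopsis, state that the main 6-month negative binomial model for fall rates includes baseline fall history as a pre-specified covariate, defined and coded as for the subgroup analysis, and that the unadjusted rate ratio is reported as a supporting result. Give the item's recall period and coding there or in the SAP. If the SAP already includes the term, confirm this and bring the protocol wording into line.

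The cost is one sentence in each place, with no new data, provided the item planned for the subgroup analysis is collected before randomisation as its name implies. The change should be fixed before any outcome data are seen by arm.

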### **7.3 Economic evaluation**

Economic evaluation will take a health and community care funder perspective and will aim to establish the cost-effectiveness and cost-utility of the Active Women over 50 intervention compared to waitlist control. We will calculate intervention delivery costs and community services and health service utilisation costs during the trial period for both groups. Using mean costs and mean health outcomes in each trial arm, the incremental cost per 1) additional person increasing physical activity by 2000+ steps/day, 2) additional fall prevented, 3) additional person achieving a meaningful improvement in physical function, and 4) quality-adjusted life years (QALY) gained of the intervention group compared with control group, will be calculated. Bootstrapping will estimate a distribution around costs and health outcomes and will be used to calculate the confidence intervals around the

incremental cost-effectiveness ratios. The results will be plotted on the cost-effectiveness plane, and as cost-effectiveness acceptability curves.

A range of additional sensitivity analyses will be conducted to determine the impact on the ICER of various assumptions within the economic evaluation, such as different costing methods and strategies for handling missing data.

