### 6.3 Cost-effectiveness outcomes

The cost of delivering the intervention and total costs of health and community service utilisation will be calculated for the cost-effectiveness analysis. Intervention costs will be estimated based on trial records where the resources required to implement the intervention will be recorded (e.g. staff time, any additional non-staff resources) and costed using appropriate wage rates and other relevant cost data. Healthcare and community-service utilisation will be collected over the trial period (6 months) on a monthly basis and costed using standard cost data such as IHPA, NHDC and Medicare unit costs.

The main effectiveness outcomes of the economic evaluation will be physical activity (average steps per day measured with an ActiGraph), falls, physical function, and utility-based quality of life six months after baseline.

Utility-based quality of life will be measured using the EQ5D-5L and the health utility score, which is expressed as an index value for health, will be calculated from the 5 questions using published Australian scoring algorithms. The scores fall on the 0.0 (dead) to 1.0 (perfect health) value scale.

Quality-adjusted life years (QALYs) will be calculated using the health utility score at baseline and 6-month follow-up. The number of QALYs gained or lost over the 6 months of follow-up will be calculated by multiplying the time spent in the health state by the relevant health utility score.

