## **7. STATISTICAL METHODS**

### **7.1 Sample Size**

A sample size of 1000 people (500/group) will provide 90% power to detect a between-group difference of 1000 steps/day (SD 4200), assuming 25% dropouts, alpha 5%. The sample size calculation was undertaken using the `sampsi` command in Stata.

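### Incremental QALYs are taken from arm means without baseline utility as a covariate, which loses precision, and an ICER confidence interval is promised unconditionally

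*Protocol*

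**What the plan says.** Section 7.3 of the protocol states the estimator for four incremental ratios, of which the fourth is cost per QALY gained: "Using mean costs and mean health outcomes in each trial arm, the incremental cost per 1) additional person increasing physical activity", and so on through the list. For uncertainty it says: "Bootstrapping will estimate a distribution around costs and health outcomes and will be used to calculate the confidence intervals around the" incremental ratios. It adds a graphical display: "The results will be plotted on the cost-effectiveness plane, and as cost-effectiveness acceptability curves". The sensitivity analyses are given by example, "such as different costing methods and strategies for handling missing data"; baseline adjustment is not among the examples.

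Section 6.3 defines the QALY: "Quality-adjusted life years (QALYs) will be calculated using the health utility score at baseline and 6-month follow-up", with QALYs gained or lost over the 6 months obtained as follows: they "will be calculated by multiplying the time spent in the health state by the relevant health utility score".

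Section 7.2, on the clinical analyses, says: "Continuous secondary outcomes will be analysed using linear regression adjusting for the corresponding baseline measure of the outcome variable as appropriate". EQ-5D-5L quality of life is one of the secondary outcomes in Table 2.

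**The concern.** The same instrument is handled in two ways. As a clinical outcome, EQ-5D-5L falls under the baseline-adjusted regression of section 7.2. As the source of the QALY, it is compared through arm means. Baseline utility is a component of the QALY, so a chance difference between arms at baseline carries straight into the QALY difference and adds to its variance. Regression on baseline utility would remove that component.

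The second issue is the interval on the ratio. Over half a year the QALY difference will probably be small; section 2.1 itself reports that the team's earlier review found no evidence that health coaching affects quality of life. When some bootstrap QALY differences are positive and others negative, a negative ratio can mean cheaper and better or dearer and worse, and ordered limits of the ratio no longer rank the results.

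Cost-effectiveness is part of secondary objective 5, which is meant to guide scale-up, so avoidable noise and an unreadable interval both matter there.

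**Working it through.** **The plan's own figure.** Section 7.1 says that 1000 women "will provide 90% power to detect a between-group difference of 1000 steps/day (SD 4200), assuming 25% dropouts, alpha 5"%. With a two-sided test, n per arm = 2 × (1.960 + 1.282)² × 4200²/1000² = 370.7, so 371. Then 742/0.75 = 989.3, so 990, and 1000 reproduces. With 500 × 0.75 = 375 completers per arm the power is 90.3%. The protocol gives no utility SD, no correlation and no economic power, so everything below on size is by assumption.

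**Assumed inputs.** Utility SD s of 0.15 or 0.20, equal at both visits; correlation r between baseline and 6-month utility of 0.3 to 0.7; true utility gain at 6 months of 0.01 to 0.03; 375 per arm.

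**QALY as area under the curve.** QALY = 0.25 × (u0 + u6).
- Unadjusted SE = 0.25 × s × sqrt(2 + 2r) × sqrt(2/375)
- SE adjusted for u0 = 0.25 × s × sqrt(1 - r²) × sqrt(2/375)
- Ratio = sqrt(2/(1 - r)), whatever s and the sample size

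| r | Ratio | Simulated ratio |
|---|---|---|
| 0 | 1.41 | |
| 0.3 | 1.69 | 1.70 |
| 0.5 | 2.00 | 1.99 |
| 0.7 | 2.58 | 2.64 |

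The simulation used 375 per arm and 4000 replicates. If the baseline SD is 0.8 or 1.25 times the 6-month SD, the ratio at r = 0.5 becomes 1.80 or 2.25.

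**QALY as change from baseline.** QALY = 0.25 × (u6 - u0). The unadjusted variance now has 2 - 2r in place of 2 + 2r, and the adjusted variance is unchanged, so the ratio is sqrt(2/(1 + r)): 1.24, 1.15 and 1.08 at r = 0.3, 0.5 and 0.7. The two constructions differ by 0.5 × u0. Once u0 is a covariate they give the same arm coefficient, so adjustment also makes the choice between them immaterial.

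**What this does to the bootstrap (area under the curve).** The expected QALY difference is d = 0.25 × gain, and the share of negative differences is about Φ(-d/SE).

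| s | Gain | r | SE unadjusted | SE adjusted | Negative, unadjusted | Negative, adjusted |
|---|---|---|---|---|---|---|
| 0.15 | 0.02 | 0.5 | 0.0047 | 0.0024 | 15% | 1.8% |
| 0.15 | 0.02 | 0.7 | 0.0051 | 0.0020 | 16% | 0.5% |
| 0.20 | 0.02 | 0.5 | 0.0063 | 0.0032 | 21% | 5.7% |
| 0.20 | 0.01 | 0.5 | 0.0063 | 0.0032 | 35% | 21% |

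For s = 0.15 and gain 0.02, d = 0.005. A baseline imbalance of one standard error shifts the QALY difference by 0.25 × (1 + r) × s × sqrt(2/375) = 0.0041 at r = 0.5 and 0.0047 at r = 0.7.

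**The ratio interval, as illustration only.** With s = 0.20, gain 0.02, r = 0.5, an assumed incremental cost of 200 (SE 150) and unadjusted means, the 2.5th and 97.5th percentiles of the simulated ratio were about -336,000 and +392,000 per QALY.

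**The case against.** The strongest reply is that section 7.3 speaks of means, not of unadjusted means, and that the covariates of a QALY regression are normally settled in a statistical analysis plan, which is not shown. The list of sensitivity analyses is also open-ended. This has some force: nothing excludes adjustment. But section 7.3 does name a method, and arm means are its ordinary reading. Replacing it with a regression on a variable already in hand is a concrete improvement, not a request for missing detail.

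Several stronger readings are tempting, and the protocol does not support them.
- A reader might infer that baseline utility is ignored. It is not: it enters the QALY and is only unused as a covariate.
- A reader might infer that the QALY error at least doubles. With equal SDs that requires r of 0.5 or more and an area-under-the-curve QALY. The protocol gives no correlation, and its reference to QALYs gained or lost can be read as change from baseline.
- A reader might infer that baseline imbalance biases the result. Randomisation makes the arm-mean difference unbiased, and the planned bootstrap already reflects chance imbalance as sampling error.
- A reader might infer that uncertainty in the economic evaluation cannot be interpreted. The plane and acceptability curves are planned and do not need the ratio interval. Section 7.3 does not specify percentile limits either. What stands is that the curves, if built on arm means, carry the same excess variance.

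**Conclusion.** The point holds as a modest, nearly free improvement to a secondary analysis. Section 7.3 leaves precision unused in the QALY difference: a factor of about 1.7 to 2.6 in the standard error under an area-under-the-curve QALY, equal SDs and an assumed correlation of 0.3 to 0.7, or about 1.1 to 1.2 under a change-from-baseline QALY. The factor does not depend on the number of completers. It does not extend to falls, responder outcomes or costs.

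Separately, the unconditional commitment to an ICER interval is unsafe when the QALY difference is near zero. Adjustment lessens that problem but does not always remove it: with SD 0.20, r = 0.5 and a gain of 0.01, about 21% of replicates would still be negative. The reporting condition is therefore needed as well as the covariate.

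**What to change.** In section 7.3, or in the analysis plan before unblinded analysis:
- Estimate incremental QALYs by regression on arm and baseline EQ-5D-5L utility, refitted in each bootstrap sample jointly with costs.
- State the QALY formula in section 6.3.
- Base uncertainty on incremental net benefit and the acceptability curves already planned, both from the adjusted replicates.
- Report an ICER interval only when the replicates lie essentially in one quadrant of the plane; otherwise give the plane and the curves alone.

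The cost is a few lines of text and code. No new data are needed, and settling it in advance removes a later choice between adjusted and unadjusted results.

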## **8 ADVERSE EVENT REPORTING**

### **8.1 Definitions**

Adverse events (AEs) are defined as incidents in which harm resulted to a person receiving health care” (AIWH <http://www.aihw.gov.au/haag11-12/adverse-events/>; accessed 2015.02.19). For the purpose of the Active Women over 50 trial, an AE is defined as an unwanted and usually harmful outcome (e.g. fall, seizure, cardiac event). The event may or may not be related to the intervention, but it occurs while the person is participating in the intervention i.e. while they are doing physical activity. Adverse events will be categorized as minor AEs (MAEs) or serious AEs (SAEs). A MAE is defined as an incident that occurs while the person is participating in the intervention that results in no injury or minor injury. For example, a fall where the person sustains a small cut or bruise that requires none or minor medical intervention. A SAE is defined as an incident that occurs while the person is participating in the intervention that results in death, serious injury or re-hospitalisation. Examples of SAEs are:

- Death
- Myocardial infarction
- Serious falls
- Serious fractures

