## **6.6 Trial Closure**

Participants will be followed up for 6 months after randomisation. Intervention group participants who consent to the additional follow-up measurement will be followed up for 12 months after

randomisation. Adverse events such as exercise related falls, musculoskeletal injury or cardiovascular events will be monitored by questions in the monthly health diaries..

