### **8.2 Assessment and Documentation of Adverse Events**

The Research Manager will be notified within 12 hours of any research staff member witnessing or becoming aware of a participant reporting an AE (e.g. through monthly health diaries, phone calls, texts, emails, communication from someone known to the participant). The research staff member will complete an AE data form within 24 hours of knowing about the AE. If a SAE occurs, the Research Manager will notify the lead investigator within 48 hours.

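### Section 8.1 sorts adverse events into two classes that neither cover every event nor exclude each other, because the minor class is worded by injury alone

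*Protocol*

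**What the plan says.** Section 8.1 of the protocol first says what counts as an event: "an AE is defined as an unwanted and usually harmful outcome (e.g. fall, seizure, cardiac event"). It then fixes the number of classes: "Adverse events will be categorized as minor AEs (MAEs) or serious AEs (SAEs").

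- **Minor.** The event occurs while the person is "participating in the intervention that results in no injury or minor injury". The illustration is "a fall where the person sustains a small cut or bruise that requires none or minor medical intervention".
- **Serious.** The event occurs while the person is "participating in the intervention that results in death, serious injury or re-hospitalisation". Four examples follow: death, "Myocardial infarction", serious falls and serious fractures.

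Section 6.6 names the risks to be watched: "Adverse events such as exercise related falls, musculoskeletal injury or cardiovascular events will be monitored by questions in the monthly health diaries".

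Section 8.2 sends every AE to the Research Manager within 12 hours, with a data form within 24 hours. A further step depends on the grade: "If a SAE occurs, the Research Manager will notify the lead investigator within 48 hours". Section 8.3 lists the grade, minor or serious, among the items recorded. Section 8.4.1 says that SAE reporting relies on the definition in section 8.1, and it sets up an independent DSMB to monitor adverse events, without limiting that role to serious ones.

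**The concern.** The minor class reads as if it had been written for falls. Its only criterion is the degree of injury, and its only illustration is a fall. Yet the AE definition and section 6.6 both include medical events that need involve no injury at all. For these, the absence of injury says little about how grave the event was, but under the wording it is enough to satisfy the minor class.

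The two classes also leave a gap between minor and serious injury, although staff must choose one or the other.

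The grade has a consequence. It decides whether the lead investigator must be told, and which events enter SAE reporting. If two staff members can reasonably grade the same event differently, or if the definition and its examples give different answers, SAE counts will not be consistent across participants.

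**Working it through.** No figure in the protocol bears on this point, so there is nothing to recompute. The check is to put each type of event through the section 8.1 wording, then through the section 8.2 notice rule.

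The inputs are the minor criterion, the serious criterion and the SAE example list (all section 8.1), and the notice rule (section 8.2). Every case assumes that the event falls within the period in which section 8.1 counts events.

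| Case | Meets minor wording? | Meets serious wording? | On SAE example list? | Result |
|---|---|---|---|---|
| A. Seizure; no injury, death or re-hospitalisation | Yes | No | No | Minor; no required notice to the lead investigator |
| B. Cardiac event other than infarction; no injury, death or re-hospitalisation | Yes | No | No | Minor; no required notice |
| C. Myocardial infarction, survived, uninjured, no re-hospitalisation | Yes | Only if read as a serious injury | Yes | Minor by wording, serious by example |
| D. Seizure or cardiac event, uninjured, re-hospitalised | Yes | Yes | Only if an infarction | Meets both wordings |
| E. Injury more than minor but not serious, no re-hospitalisation | No | No | No | No class |

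**Not exclusive.** In case D both definitions are satisfied, because the minor wording does not exclude events that meet another serious criterion. A reader would presumably let the serious class prevail, but the text does not say so. In case C the definition and the example list conflict.

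**Not exhaustive.** In case E neither definition is met. A fracture managed without admission shows the difficulty. It is hard to equate with the small cut or bruise of the minor illustration, while the SAE list qualifies fractures as serious ones, which suggests that some are not. Nothing in section 8.1 says where the others go.

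**Examples against criteria.** Of the three AE examples in section 8.1, two (seizure and cardiac event) are not injuries. Of the three risks named in section 6.6, one (cardiovascular events) is not. The serious definition has no element for an acute medical event as such. It reaches one only through death, re-hospitalisation or a stretched reading of serious injury. The infarction example shows that the protocol means at least some such events to count as serious, but the definition does not deliver that.

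**Does this depend on other wording in the section?** Re-hospitalisation does not literally cover a first admission of a community-dwelling woman, and the class of an admitted event is unclear for that reason too. That is a separate matter. If the word were read as any admission, cases A, B, C and E would be unchanged, since none involves admission. Case D would still meet both wordings.

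**The case against.** The strongest case on the other side has four parts.

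1. **The split does not turn on injury alone.** Death and re-hospitalisation also make an event serious, and infarction is serious by name. This stands. A reader might infer that seizures and cardiac events in general are graded minor. The protocol does not support that: only those without injury, death or re-hospitalisation, and other than infarction, fall there.

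2. **A minor grade does not mean no oversight.** Every AE reaches the Research Manager within 12 hours and is documented within 24. The items in section 8.3 include the type of event, injuries sustained, fracture type and how the event was managed, so it could be regraded later. The DSMB monitors adverse events at large. Section 8.2 does not forbid telling the lead investigator about other events. All this stands, and it limits the consequence.

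3. **The lower class may be deliberate.** For a programme of coaching, messages, a website and an online group, placing events with no death, serious injury or admission in the lower of two classes is defensible. This stands in part. The protocol gives no correct class for cases A and B, so they cannot be called misclassified. It does not answer case C, where the protocol contradicts itself, or case E, where it gives no answer.

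4. **Some judgement about what is serious is normal in any grading scheme.** True, but judgement operates between classes that meet. Here they leave a gap in one place and overlap in another.

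A reader might also infer that DSMB stopping rules would be distorted. Section 8.4.1 says only that these will be determined in advance. They are not shown, and nothing says that they use SAE counts.

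**Conclusion.** Wrong as written; low severity. The two classes in section 8.1 are neither exhaustive nor mutually exclusive, and the definition conflicts with its own example for a survived, uninjured infarction. Two things are affected: the required notice to the lead investigator and the consistency of SAE counts. General oversight is not lost, and an effect on stopping rules is possible only if those rules rest on SAE counts.

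The number of events involved cannot be derived, because the protocol gives no expected rates of seizure, cardiac event or intermediate injury. The conclusion rests on a literal reading of section 8.1, and on section 8.4.1 pointing back to that definition for SAE reporting. The University's operating procedure cited there is not shown and might give staff further guidance.

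The documents do not support going further and saying which medical events or which fractures ought to be serious.

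**What to change.** Change the wording of section 8.1 and carry it into the AE form:

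- Define a minor AE as any AE that does not meet the SAE definition. This alone closes the gap in case E and removes the overlap in case D.
- Reconcile the SAE definition with both example lists, so that it states how medical events without injury, and injuries between minor and serious, are classed. Infarction should then follow from the definition as well as from the list.

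The criteria themselves are for the sponsor and the DSMB to set.

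The cost is an amendment to the text and the form, with no change to data collection. The downside is that a few more events may be graded serious and passed to the lead investigator. Events already recorded could be regraded from the items in section 8.3.
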